1.0 Objectives*

1.1 The purpose of our research is to compare the effectiveness of 40mg/ml sodium thiosulfate (STS) solution to normal saline (0.9% sodium chloride) when injected intralesionally for the treatment of calcinosis cutis. Our specific aim is to assess the response of dystrophic and idiopathic calcinosis cutis to the injections of sodium thiosulfate in our patients.

1.2 Our hypothesis is that three injections of STS, each spaced one month apart, will significantly improve our patients' calcinosis cutis condition to a point where they are effectively clear or have a 2-point improvement in their Physician Global Assessment (PGA) scores when compared to normal saline.

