8.0 Study Endpoints*

8.1 Study endpoints:

- Primary:
 - Change in size of study lesions
 - Change in Physician Global Assessment
 - Visual Analog Scale of pain of injection
- Secondary:
 - Adverse Events

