- During each visit subjects will be monitored for any adverse events and asked about any potential adverse events since the last visit. Any adverse events will be logged on the Adverse Events Form (see attached).
- Visit 1 will be followed with a 48-hour post-treatment phone call to assess for any adverse events.
- After all subjects have completed their participation, photographs of lesions will be reviewed by [name] who will fill out the Independent Observer Case Report Form (see attached) for each visit. He will be blinded as to which lesions received which treatment and at which visit in the study the lesions were photographed.
- Screening and consent
 - First, each subject will sit down with the principal investigator to discuss the study in depth and review the screening criteria. After all risks, benefits, alternatives, and questions have been discussed consent will be obtained.
 - After the informed consent form is signed, the eligibility screening portion of the case report form will then be filled out by the principal investigator with the research subject. If necessary, a pregnancy test will be performed.

A Comparative Study of the Efficacy of Intralesional Sodium Thiosulfate Versus Intralesional Normal Saline for the Treatment of Dystrophic and Idiopathic Calcinosis Cutis, A Double-Blind Randomized Placebo-Controlled Trial

- Solution preparation
 - 50 ml vials of sodium thiosulfate (250mg/ml) will be used for preparation of the treatment solution.
 - The solution from the bottle will be diluted in a ratio of 1 part sodium thiosulfate 250mg/ml to 5.25 parts sterile water to yield a 40mg/ml solution of sodium thiosulfate.¹⁴ This is done to make the final solution as close to isotonic as possible.
 - 30 ml vials of sodium chloride 0.9% will be used for the control treatment.
 - The solutions will be drawn up in 1 cc syringes utilizing a 25g needle by [name]. The needle will then be replaced with a capped 30g ½ inch needle.
 - All solutions will be drawn up by [name] the day of use and discarded immediately after use.
 - Treatment and control will be randomized once for the entire study and all subjects based upon a one-time flip of a coin as follows:
 - If coin flip is heads: all “A” lesions will receive STS and all “B” lesions will receive normal saline
 - If coin flip is tails: all “A” lesions will receive normal saline and all “B” lesions will receive STS
 - This result will be recorded on the Unblinded Treatment Document (See attached).

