 - [name] will not be notified of the result until after completion of the study so as to keep him blinded.
 - The syringes will be labeled with an “A” or “B” label for blinding by [name], or [name].

- Administration of study solutions
 - A volume of 0.1 ml/cm² of normal saline or STS will be injected into each lesion. Therefore, a maximum of 0.4ml of 40mg/ml STS or 16mg of STS (given maximum size of 2 cm x 2 cm) will be used per visit per subject.
 - The same treatment lesion will be injected only with STS every injection and the same control lesion will be injected only with normal saline (0.9% sodium chloride) every injection. In other words, “Lesion A” will always be injected with solution A and “Lesion B” will always be injected with solution B.
 - [name], a board-certified dermatologist, will be administering all injections of STS and normal saline to minimize risks for subjects.

- Disposal Protocol:
 - After use, needles will be disposed of in red sharps container according to UCF Health policy
 - After use, urine samples will be disposed of in the toilet according to UCF Health policy

A Comparative Study of the Efficacy of Intralesional Sodium Thiosulfate Versus Intralesional Normal Saline for the Treatment of Dystrophic and Idiopathic Calcinosis Cutis, A Double-Blind Randomized Placebo-Controlled Trial

9.3 Risk Management:

- Subjects will be directly observed during the administration of the STS and normal saline for any adverse events. An anaphylaxis kit is available in clinic should any subject experience such an event. The principal investigator is certified in basic cardiopulmonary life support and an AED is present in the facility. Subjects will be provided with the phone number of the PI should any issues related to participation in the study arise.
- Sodium thiosulfate is currently FDA-approved for as an antidote in the treatment of cyanide poisoning. FDA phase III studies are currently being conducted for use in calciphylaxis.
- 0.9% Sodium chloride is currently FDA-approved for parenteral replenishment of fluid, diluting or dissolving drugs for intravenous, intramuscular or subcutaneous injection, according to instructions of the manufacturer of the drug to be administered.
- Sterile water is currently FDA-approved as a solvent or diluent vehicle for parenterally administered drugs or solutions and as a source of water for parenteral fluid replenishment after suitable additives are introduced.

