20.0 Resources Available

20.1 [name] has significant prior experience conducting research, knowledge of the regulations and customs at UCF Health, and works regularly with patients performing dermatologic surgery. All injections will be administered by [name]. [name] has extensive experience conducting clinical research. In addition, the medical students involved in the project will be able to help significantly. Through the FIRE project [name] will be able to assist with data analysis.

20.2 Resources available to conduct research:

- The study's small sample size (N=10) makes it likely that the required number of subjects will be recruited in less than 8 months. [name] combined see more than half this number of patients with calcinosis cutis annually. In addition, the rheumatologists at UCF Health see at least as many patients with calcinosis cutis. Finally, recruiting through the local dermatology society and advertising should supplement the numbers needed to complete the study.
- Research will be conducted during [name] administrative time or on the weekend.
- The study will be will be conducted at the UCF Health Clinic, see section 19. Setting.
- While the chances of a research related injury are extremely rare, subjects will be required to have health insurance in order to participate in this study. Treatment for research related injury will be made available,

A Comparative Study of the Efficacy of Intralesional Sodium Thiosulfate Versus Intralesional Normal Saline for the Treatment of Dystrophic and Idiopathic Calcinosis Cutis, A Double-Blind Randomized Placebo-Controlled Trial

however costs associated with this treatment will be billed to the subject's insurance company. Costs not covered by the subject's insurance company will be the subject's responsibility.

- All individuals assisting in the research study will be provided a copy of the IRB-approved protocol and given the opportunity to meet with the principal investigator before recruitment begins. The principal investigator, [name], will be responsible for informing all research staff of their research-related duties during a personal meeting or via phone or email. The contact information of the principal investigator and co-principal investigator will be distributed to all research staff and the subjects.

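### One injector gives both solutions under a single fixed A/B code: if the solutions differ in pain the code could be inferred, and the plan neither keeps that person from rating nor says which PGA decides efficacy

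*Combined protocol and SAP*

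**What the plan says.** Section 9.2 (Administration of study solutions) gives all injecting to one person, "a board-certified dermatologist, will be administering all injections of STS and normal saline to minimize risks for subjects". Section 20.1 repeats this: "All injections will be administered by", followed by a removed name.

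Allocation is described under Solution preparation in 9.2: "Treatment and control will be randomized once for the entire study and all subjects based upon a one-time flip of a coin". The letter never changes meaning within a subject either: "The same treatment lesion will be injected only with STS every injection", and likewise for the saline lesion. Section 1.2 plans "three injections of STS, each spaced one month apart".

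Section 8.1 lists three primary endpoints: change in lesion size, change in PGA, and "Visual Analog Scale of pain of injection".

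At each of the four visits, 9.2 calls for the lesions to be assessed on the Case Report Form. Those lines name no person or role. This is not a redaction, since they contain no removed-name marker.

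There are three blinding safeguards. Syringes carry only A or B, and the coin result is withheld from one person until the study ends. The third is an independent observer who rates the photographs after all subjects have finished: "He will be blinded as to which lesions received which treatment and at which visit in the study the lesions were photographed". Section 11.1 plans Cohen's kappa for PGA, which implies two PGA ratings, but no section says which one the efficacy comparison uses.

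**The concern.** Withholding the coin result stops a person from being told the code. It does not stop that person from working it out. The injector gives A and B to the same subject at the same visit and is present for the reaction to each. Because one code covers the whole trial, what is seen in one subject bears on every other, and a single correct inference unblinds every lesion.

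This matters only if the inference reaches an outcome rating. The hypothesis in 1.2 rests on PGA, a physician's judgement. A rater who believes that one letter is STS could drift in the same direction in every subject. With a target of 10 eligible subjects, a consistent drift could weigh heavily. The plan does not require the on-site rater to be someone other than the injector or the person who records pain. It also leaves open whether efficacy rests on the on-site PGA or on the rating by the observer who sees only photographs.

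**Working it through.** The documents give no figure for this point, so there is none to reproduce. The numbers below illustrate how fast a code could be inferred if the solutions differ in pain.

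**Inputs from the documents**
- Target of 10 eligible subjects (4.1).
- Three injection visits, at weeks 0, 4 and 8 (7.1, 9.2), each with one A and one B injection.
- Hence up to 10 × 3 = 30 side-by-side pairs, seen by one injector under one code.

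**Assumptions, none from the documents**
- q is the chance that STS is the more painful injection in a pair. I take 0.5 (no difference) to 0.8.
- The injector expects STS to be the more painful solution, and takes as STS the letter that hurt more in most pairs.

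**Formula.** For odd n independent pairs,

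P(correct) = Σ C(n,k) q^k (1−q)^(n−k), summed over k from (n+1)/2 to n.

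For even n, half the probability of a tie is added.

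**Nine independent pairs, q = 0.7:** the terms for k = 5 to 9 are 0.1715 + 0.2668 + 0.2668 + 0.1557 + 0.0404 = 0.901.

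**Allowing for correlation.** The same two lesions are injected three times, so repeats in one subject may carry the same information. At the extreme of full correlation, nine pairs from three subjects count as three: P = 3q²(1−q) + q³. At q = 0.7 this is 0.441 + 0.343 = 0.784.

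| Evidence seen | q = 0.5 | 0.6 | 0.7 | 0.8 |
|---|---|---|---|---|
| 9 independent pairs | 0.50 | 0.73 | 0.90 | 0.98 |
| 9 pairs from 3 subjects, repeats fully correlated | 0.50 | 0.65 | 0.78 | 0.90 |
| 30 independent pairs | 0.50 | 0.86 | 0.99 | >0.99 |
| 30 pairs from 10 subjects, repeats fully correlated | 0.50 | 0.73 | 0.90 | 0.98 |

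The single code is what lets evidence pool. With a separate code for each subject, only that subject's own three pairs would inform (at most 0.65, 0.78 and 0.90 for q = 0.6, 0.7 and 0.8), and a correct guess would unblind only that subject.

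**When the inference could act.** At each treatment visit, 9.2 lists photographs, then assessment, then injection. Week 12 has assessment but no injection. If that order is kept, a visit's ratings come before that visit's injections. What remains is carry-over: from a subject's earlier visits to later ones, including Week 12 after all three injections, and from earlier subjects to later ones.

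**The case against.** The strongest reply is that no pain difference is documented. Section 14.1 lists minimal pain for either solution alike. Section 9.2 dilutes STS to bring it near isotonic and limits it to 0.4 ml per visit. The pain-withdrawal rule in 8.2 names neither solution. Making pain an endpoint asks whether the solutions differ; it does not predict that they do. All of this stands. With q = 0.5 nothing is learned by this route, and near-isotonicity neither proves nor excludes equal pain.

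The second reply is that the injector may not be the on-site rater. Names are removed and the Case Report Form is not supplied, so this cannot be settled either way. The point is only that the plan does not separate the roles.

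The third is that assessment is already listed before injection. That is correct and reduces the risk to carry-over.

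The fourth is that the independent observer never sees an injection, so an on-site PGA effect can be checked against that rating. This also stands. A reader might infer that a positive PGA result could not be told apart from bias. The documents do not support that, because the comparison rating is already planned for every visit. The gap is that the plan does not say which rating decides. In addition, 9.2 has the lesions marked A and B before they are photographed and describes no masking of the letters, so a leaked code could reach that observer too.

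**Conclusion.** The concern holds as a conditional risk to blinding. One injector, both solutions in every subject, one unchanging code and a pain endpoint are all stated. No rule keeps the injector or pain recorder from rating on site, and no rule says which PGA decides efficacy.

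The size depends on assumptions. For q from 0.5 to 0.8, the chance of reaching the right letter after nine pairs runs from 0.50 to 0.98 if pairs are independent, and from 0.50 to 0.90 if repeats within subjects are fully correlated. Both ranges also require the injector to expect STS to hurt more.

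A reader might go further and infer that STS is the more painful solution, that the injector does the rating, or that blinding will fail. The documents establish none of these. Nor do they say how lesion size is measured, so nothing here rests on the measuring method. The case for change is that a known route to bias can be closed cheaply with ratings and staff the trial already has.

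**What to change.** **In 8.1 and 11.1:** make the independent observer's blinded photograph PGA the rating that decides the PGA efficacy conclusion, and report the on-site PGA as supportive. Mask or recode the A/B letters on the photographs before review.

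**In 9.2:** state that on-site size and PGA are rated by an existing team member who does not inject, does not record or see the pain scores, does not prepare or label syringes, and does not otherwise know the key. The last two conditions matter: without them, the change could replace a rater who might infer the code with one who knows it. Make the listed order, assessment before injection, binding.

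**Optional:** before the key is opened, record which letter the injector and the on-site rater believe is STS. Ask early as well as at Week 12, because a late guess may reflect visible efficacy rather than pain.

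**Cost:** protocol and form wording, masking of photographs, and a division of roles within the present team. The downside is that photographs show deep or palpable deposits less well than examination does, which is why the on-site PGA should still be reported.

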9.4 Data to be collected

- Age
- Gender
- Race
- Ethnicity
- Medical History
 - Past Medical and Surgical History
 - Medications

A Comparative Study of the Efficacy of Intralesional Sodium Thiosulfate Versus Intralesional Normal Saline for the Treatment of Dystrophic and Idiopathic Calcinosis Cutis, A Double-Blind Randomized Placebo-Controlled Trial

- Allergies
- Social History
 - Tobacco use
 - Alcohol use
- Laboratory Results
- Size of lesions
- Visual Analog Scale for Pain (VAS Pain)
- Physician Global Assessment (PGA)
- Photographs will also be taken of all study lesions during every assessment and will be stored directly in the password protected HIPAA compliant network drive for clinical research at UCF Health. Though the photos will not contain any identifiers, subjects are potentially identifiable from the photos and thus they will be stored in the password protected HIPAA compliant network drive for clinical research at UCF Health.

10.0 Data and Specimen Banking*

10.1 There will be no data or specimen banking for future use.

11.0 Data Management* and Confidentiality

11.1 Data will be reported descriptively [mean and standard deviation; median (min-max) and frequency and percentage]. Interrater reliability of PGA will be conducted using Cohen's kappa statistic. As a second step, differences across times and between groups will be explored with non-parametric tests, such as Kruskal-Wallis test and the Mann Whitney U test. Statistical significance will be tested at $p < .05$.

The data will be analyzed for significant differences with aid of a statistician. The results of the data analysis will be graphed for each parameter.

11.2 For our study, we will recruit up to 12 adult male and female volunteers ages 18 years and older. This number is estimated from clinical knowledge of the cases that present to treatment on an annual basis at the research site. Furthermore, a review of the existing literature suggests that the targeted sample size is commensurate to other published studies.^{3,4,13,5-12}

11.3 Data will be managed as follows:

- Data will be stored in the secure HIPAA-compliant database called REDCap.
- Unique identifiers will be created using sequential numbers (i.e. 1, 2, 4 etc.).
- No data collection instrument in REDCap will contain identifying information
- The Screening and Enrollment Log, Drug Accountability Log, Unblinded Treatment Document, Demographics Forms, Medical History Forms, Eligibility Forms Case Report Forms, Independent Observer Case Report Forms, Adverse

A Comparative Study of the Efficacy of Intralesional Sodium Thiosulfate Versus Intralesional Normal Saline for the Treatment of Dystrophic and Idiopathic Calcinosis Cutis, A Double-Blind Randomized Placebo-Controlled Trial

Event Forms (see attached documents) will all be stored in the regulatory binder in a locked drawer in a locked room at UCF Health. Only [name] will have access to this locked drawer.

- Photographs will be taken with a UCF Health digital camera. The photographs will then be transferred to a folder on a password protected HIPAA compliant network drive for clinical research at UCF Health. After transfer of photographs to clinical research folder they will be deleted from the camera. Photographs will be labeled with subject ID number and visits number (i.e Subject 01 3-month)
- A subject ID assignment list (see attached document “Subject ID Assignment List”) that links the subject name and contact information with their unique identifier will be stored in a separate folder in locked drawer in a locked room at UCF Health. Only [name] will have access to this locked drawer.
- Identifying information such as the “Subject ID Assignment List” will only be accessed by the PI and co-PIs for initial entry. It is possible the identifiable information may be referenced if questionable data are detected during data analysis (e.g.: number out of range, missing data).
- The “Screening and Enrollment Log” and the “Subject ID assignment List” will both be disposed of in a HIPAA-compliant shred bin at the completion of the study.
- Informed consents and HIPAA authorizations will be stored in locked drawer in a locked room at UCF Health and kept for a minimum of six years after the conclusion of the study (per UCF data retention policies.)
- Only de-identified data will be used and exported for analysis.
- De-identified data and photographs will be stored for a minimum of five years after the conclusion of the study (per UCF data retention policies).

11.4 Data will be verified for correctness by 2 of the investigators after entry to REDCap.

11.5 Not applicable. See above section for how data will be handled study-wide as this is a single center, single site study.

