2.0 Background*

2.1 Calcium plays an important role in the growth and differentiation of the skin.¹ As a result, dysregulation of calcium can have dermatologic consequences. One of these consequences results in a condition known as calcinosis cutis. This is an uncommon dermatologic condition in which calcium deposits are formed in the skin and result in cutaneous calcification. There are various types of this condition, including dystrophic, metastatic, iatrogenic, and idiopathic.^{1,2} Our research, however, will be focused on dystrophic and idiopathic calcinosis cutis. These forms often present in areas of the skin that have been previously damaged, and these patients often have no fundamental metabolic irregularities in calcium regulation.¹ It is believed that the calcification develops when an associated disease causes tissue damage. This damage allows calcium to move into the affected area and crystallize.¹ Another line of thinking is that the acidity which follows cell damage may have an effect on local calcium inhibitory processes.¹ Dystrophic Calcinosis cutis is commonly associated with autoimmune connective tissue disorders such as scleroderma, dermatomyositis, and cutaneous lupus erythematosus.^{1,2} Other etiologies may include panniculitis, genetic disorders, infections, neoplasms, and trauma¹.

2.2 There are a variety of potential treatments for dystrophic calcinosis cutis which depends upon factors such as size, location, and etiology. These treatments include surgical excision, bisphosphonates, warfarin, tumor necrosis factor inhibitors, among others². However, these often have varying degrees of success and none of which are FDA-approved.² One studied treatment involves the drug sodium thiosulfate. Sodium thiosulfate (STS) has been used successfully in a number of cases topically, intravenously (IV), and intralesionally by increasing the solubility of the cutaneous calcium deposits. There have been several case reports examining STS topically for several months.³⁻⁷ Potential downsides to topical treatments are that they may not penetrate the skin deep enough to affect the calcifications, and patients must strictly adhere to the application directions. Additionally, STS has been used intravenously with success.^{3,8,9} However, there have been cases of patients discontinuing IV STS due to its side effects of fatigue and nausea.¹⁰ There have also been cases in which there was a lack of response to IV STS.^{9,10}

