A Comparative Study of the Efficacy of Intralesional Sodium Thiosulfate Versus Intralesional Normal Saline for the Treatment of Dystrophic and Idiopathic Calcinosis Cutis, A Double-Blind Randomized Placebo-Controlled Trial

2.3 We wish to examine STS intralesionally (IL) since this would allow for minimization of the side effects of the IV treatment, higher local concentrations than the topical approach, and easier accessibility of the affected site(s). Intralesional STS has been used in a number of cases to treat dystrophic calcinosis cutis with great success.¹¹⁻¹³ However, from the literature, there are currently no prospective studies which compare the efficacy of STS to normal saline which is the gap in knowledge that we are attempting to address.

Our prospective study will allow us to address this gap in knowledge by comparing the intralesional administration of STS to normal saline for the treatment of dystrophic and idiopathic calcinosis cutis lesions. If successful, this study will contribute significantly to demonstrating the efficacy of IL STS for dystrophic and idiopathic calcinosis cutis and could be a stepping stone for development of more effective treatments.

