4.0 Study-Wide Number of Subjects*

A Comparative Study of the Efficacy of Intralesional Sodium Thiosulfate Versus Intralesional Normal Saline for the Treatment of Dystrophic and Idiopathic Calcinosis Cutis, A Double-Blind Randomized Placebo-Controlled Trial

4.1. We plan on enrolling 12 subjects with the aim to accrue 10 subjects who successfully screen for eligibility for the study. This number was derived on consultation with [name].

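### Section 11.1 plans no STS–saline difference with an interval, and names tests for independent groups although each subject supplies a pair of lesions

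*Combined protocol and SAP*

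**What the plan says.** The whole statistical plan is in section 11.1. It begins "Data will be reported descriptively [mean and standard deviation; median (min-max) and frequency and percentage" and adds Cohen's kappa for agreement on PGA. Then "differences across times and between groups will be explored with non-parametric tests, such as Kruskal-Wallis test and the Mann Whitney U test". The text continues "Statistical significance will be tested at" p < .05, without saying whether one- or two-sided, and closes with "The data will be analyzed for significant differences with aid of a statistician" and a graph for each parameter.

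The design in section 9.2 is within-subject: each subject has a lesion A and a lesion B. One always receives STS and the other always saline.

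On size, section 4.1 says "We plan on enrolling 12 subjects with the aim to accrue 10 subjects who successfully screen for eligibility for the study" and attributes the number to consultation. Section 11.2 bases it first on the site's annual caseload and then adds that "a review of the existing literature suggests that the targeted sample size is commensurate to other published studies". No section gives a power, target difference, SD, response rate or target precision.

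**The concern.** The hypothesis in section 1.2 is comparative: cleared lesions, or a two-point PGA gain, relative to saline. The quantity that answers it is the STS-minus-saline difference within subjects, with its uncertainty. Nothing in section 11.1 produces that. Summaries and graphs describe each group separately, kappa describes the raters, and the two named tests give p-values that ignore the pairing.

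With about ten pairs, a p-value above .05 is compatible both with no effect and with an effect worth having. Only an interval tells the two apart. The same holds for harms: adverse events are an endpoint in section 8.1, yet no interval is planned for them, and a count of zero in ten subjects is weak evidence of safety.

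**Working it through.** **Plan's own figure.** The only stated figure is 12 enrolled to give 10 eligible. With no power, effect, SD or rate behind it, there is no calculation to reproduce. What follows is what 10 pairs can show.

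**Assumptions.** n = 10 pairs (section 4.1); two-sided 5% (section 11.1 gives .05 only); paired t as an approximation; effects in SDs of the paired difference, because the documents give no SD.

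**1. Why per-group SDs are not enough.** The SD of the paired difference is √(s₁² + s₂² − 2·r·s₁·s₂). With equal SDs s this is s·√(2(1 − r)): 1.41s at r = 0 and 1.00s at r = 0.5. The within-subject correlation r is not among the planned summaries, so the paired interval cannot be recovered from them.

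**2. Precision.** Half-width = t(.975, 9)/√10 = 2.262/3.162 = 0.72 SD. For example, an observed difference of 0.7 SD gives t = 0.7 × 3.162 = 2.21 and p = 0.054, with a 95% interval of −0.02 to 1.42 SD. The p-value alone says not significant. The interval shows that a very large benefit is not excluded.

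**3. Power** (non-central t, 9 df, non-centrality δ√10):

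| True difference δ (SD) | Power, 10 pairs | Power, 12 pairs |
|---|---|---|
| 0.5 | 29% | 35% |
| 0.8 | 62% | 71% |
| 1.0 | 80% | 88% |

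At 12 pairs the half-width is 0.64 SD.

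**4. Named test against a paired test.** In simulation (4,000 runs, normal data, 10 pairs, true difference 0.8 SD of a single lesion's values):
- correlation 0.5: Mann-Whitney has 33% power and Wilcoxon signed-rank 60%;
- correlation 0: 35% and 34%.

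The correlation values are assumptions. Pairing costs almost nothing when lesions are unrelated and gains a good deal when they are correlated.

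**5. Responder outcome of section 1.2** (exact McNemar, two-sided):
- 5 discordant pairs to 0: 2 × 0.5⁵ = 0.0625, a gain of 5/10 = 50 points;
- 6 to 0: 2 × 0.5⁶ = 0.031;
- 6 to 1, also 50 points: 0.125.

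**6. Zero events in 10.** The one-sided 95% upper bound is 1 − 0.05^(1/10) = 25.9%. The upper end of the two-sided exact 95% interval is 1 − 0.025^(1/10) = 30.8%. With 12 subjects these are 22.1% and 26.5%. If the true risk were 10%, zero events in 10 would still occur with probability 0.9¹⁰ = 35%.

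**The case against.** Several points on the other side are sound, and they limit what may be inferred.

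- **Is the p-value the only tool?** A reader might infer this, but section 11.1 puts description first and calls the testing an exploratory second step. Per-group change scores and graphs show direction and rough size. Only the suspension rule in section 12.1 acts on a p-value alone. What remains is that no planned output gives the precision of the difference.
- **The list of tests is open-ended.** It is given by way of example, so a paired test is not ruled out. None is named, however, and both examples assume independent groups.
- **Is N justified by case reports?** That overstates the text. Caseload and consultation are the main grounds, and the literature is supporting. The statement "There have been several case reports examining STS topically for several months" covers the topical papers only. Of the eleven references cited in section 11.2, three titles show a count (one patient, four cases, three cases), so the claim of similar size cannot be shown false. Section 2.3 says only that "there are currently no prospective studies which compare the efficacy of STS to normal saline", not that no comparison of any kind exists. A small trial set by feasibility is legitimate, and N misses no target because none is stated.
- **Is a non-significant result the likeliest outcome?** This cannot be derived. The documents give no SD or response rate, and section 1.2 expects a large effect. At 1.0 SD the paired power is 80%.
- **Will the trial report no difference, or call the treatment safe?** The documents say neither. The most that can be said is that the results could be read that way.
- **The interval can be computed later.** True: the paired data are collected, and section 11.3 keeps them for at least five years. What is lost is pre-specification, and the reader's ability to obtain the interval from the planned report.
- **Paired figures do not describe the tests named.** Also true, as step 4 of the working shows. Adding a paired interval while keeping Mann-Whitney could give an interval and a p-value that disagree, so the test must change too.

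**Conclusion.** The point holds as a gap in analysis and reporting. Section 11.1 pre-specifies no STS–saline difference and no interval for any endpoint, names tests that ignore the pairing, and plans summaries from which the paired interval cannot be rebuilt. Sections 4.1 and 11.2 say nothing about precision.

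For ten pairs, two-sided 5%, the interval would extend about 0.72 SD either side of the estimate. A 50-point responder gain can miss p < .05, and zero events would leave a rate of roughly 26% to 31% not excluded. The SD-scale figures rest on the paired-t approximation. The 5-to-0 example also assumes that no pair favours saline.

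The documents do not support the stronger reading that the sample size is itself an error, or that a null or all-clear conclusion is planned. The change is worth making because it improves the answer to the trial's own question from data already being collected.

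**What to change.** In section 11.1, make the treatment comparison within-subject (this presumes that PGA and VAS are recorded lesion by lesion):

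- **Size change and VAS:** report the Hodges-Lehmann estimate, that is, the pseudomedian of the within-subject STS-minus-saline differences, with a 95% interval. Use the matching Wilcoxon signed-rank test in place of Mann-Whitney.
- **PGA change:** report the same estimate by a method that handles ties, and do not call the interval exact.
- **Responder outcome of section 1.2:** report the paired difference in proportions with a 95% interval for paired data, and an exact McNemar test.
- **Adverse events:** report local events per lesion and systemic events per subject, the latter not attributed to a lesion. Give exact 95% intervals for each.
- **Interpretation:** state that p ≥ .05 will be interpreted through the interval and not as absence of effect.

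Optionally, in section 11.2, say that N is set by feasibility and give the approximate paired precision at 10 pairs with its assumptions.

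The cost is a few lines of text and slightly more analysis, with no extra subjects, visits or data. If the optional sentence is added, the stated rationale for N will look less favourable.
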